## 5.1.3.3 Conjunctival Erosion

The PDS implant and/or its procedures have been associated with conjunctival erosion (defined as a full thickness degradation or breakdown of the conjunctiva). These events may be clinically relevant if the implant becomes exposed, and could be associated with an increased risk of endophthalmitis. The tissue overlying the PDS implant flange should be monitored carefully following the implant insertion and refill-exchange procedures to identify easy signs of erosion and permit early medical or surgical intervention, if necessary. After discussion with the Medical Monitor, surgical intervention (e.g., conjunctival/Tenon's capsule repair) should be performed in case of conjunctival erosion with or without exposure of the implant flange.

Close adherence to the most up-to-date PDS IFU document (e.g., appropriate incorporation of conjunctiva and Tenon's capsule in peritomy closure, appropriate placement of conjunctival sutures to avoid contact with the implant edge, etc.) is required to minimize risks of conjunctival erosion.

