#### 5.1.5.5 Recommended Management of Conjunctival Retraction or Conjunctival Erosion Cases

The recommended management of patients with conjunctival retraction or conjunctival erosion is presented in Table 6.

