# Table 6Recommended Management of Patients with Conjunctival
Retraction or Conjunctival Erosion

Event	Patient's Examination and Management Guidelines
Conjunctival Retraction	
 
Prescribe antibiotic drops as per standard of care.
 
Consult Medical Monitor for management.
 
Schedule for surgery as soon as possible.         
 
Perform conjunctival flap revision with robust undermining of the surrounding conjunctiva and Tenon's capsule and release of any traction from previous surgery before advancing healthy tissue to limbus.
 
Suture the flap with multiple interrupted sutures.
 
 
 
In case of recurrent conjunctival retraction, consider use of a split thickness corneal graft placed underneath the conjunctiva and Tenon's capsule (if corneal tissue is not available, consult Medical Monitor for advice on further management).
 

Conjunctival Erosion	
 
In case of confirmed or suspected conjunctival erosion, Prescribe antibiotic drops as per standard of care.
 
For a suspected conjunctival erosion, consider application of topical fluorescein over conjunctiva to confirm erosion on slit lamp examination using cobalt blue light.
 
Consult the Medical Monitor for management.
 
Watch and wait in case of small localized erosion without flange exposure if the surrounding tissue is well adhered to sclera and there is no evidence of an active leak.
 
Schedule for surgery in case of full-thickness erosion (i.e., exposing the flange), or evidence of an active leak with Seidel positivity.
 
Perform conjunctival flap revision with robust undermining of the surrounding conjunctiva and Tenon's capsule and release of any traction from previous surgery.
 
Suture the flap with multiple interrupted sutures.
 
In case of recurrent conjunctival erosion, consider use of a split thickness corneal graft placed underneath the conjunctiva and Tenon's capsule (if corneal tissue is not available, consult Medical Monitor for advice on further management).
 

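### Protocol Section 5.1.3.3 and Table 6 give opposite instructions for a small conjunctival erosion that leaves the flange covered

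*Protocol*

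**What the plan says.** **Section 5.1.3.3 (Conjunctival Erosion)**, among the anticipated risks of the implant, defines the event as erosion "defined as a full thickness degradation or breakdown of the conjunctiva". It asks for monitoring so as to "permit early medical or surgical intervention, if necessary". It then states that, after discussion with the Medical Monitor, surgical intervention "should be performed in case of conjunctival erosion with or without exposure of the implant flange".

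**Section 5.1.5.5** covers management of the same event: "The recommended management of patients with conjunctival retraction or conjunctival erosion is presented in Table 6".

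**Table 6, erosion row**, contains three relevant instructions:

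- The Medical Monitor is to be consulted, as in Section 5.1.3.3.
- Some eyes are to be observed: "Watch and wait in case of small localized erosion without flange exposure". Two further conditions apply, namely that the tissue around the erosion is adherent and that nothing is leaking.
- Other eyes go to surgery: "Schedule for surgery in case of full-thickness erosion (i.e., exposing the flange), or evidence of an active leak with Seidel positivity".

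The Version 5 amendment rationale lists both the risk text (Sections 5.1.3.1 to 5.1.3.6) and the management text (Sections 5.1.5.4 to 5.1.5.7) as updated in that version, and names erosion in each. Both are therefore current.

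**The concern.** The surgery sentence in Section 5.1.3.3 makes no exception for size, adherence or leakage, and it expressly includes eyes in which the flange is still covered. Table 6 takes some of those eyes and directs observation. An investigator who relies on one passage would operate, and one who relies on the other would not. Each could be said to have departed from the protocol.

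Conjunctival erosion is listed as an ocular adverse event of special interest in Section 5.2.3, and Section 5.1.3.3 says it could carry a higher risk of endophthalmitis. What is at stake is consistent care of an implanted eye.

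A second difficulty is the term *full thickness*. Section 5.1.3.3 applies it to every conjunctival erosion, whereas Table 6 equates it with exposure of the flange.

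**Working it through.** No sample size, power or error-rate calculation bears on this point, so the check is a comparison of the two texts, situation by situation. Table 6's observation instruction has five conditions: the erosion is small, it is localized, the flange is not exposed, the surrounding tissue is adherent, and there is no active leak.

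| Situation | Section 5.1.3.3 | Table 6 | Result |
|---|---|---|---|
| 1. Flange exposed | Surgery | Surgery | Agree |
| 2. Flange covered, Seidel-positive active leak | Surgery | Surgery | Agree |
| 3. Flange covered, and the other four conditions met | Surgery | Observation | **Contradict** |
| 4. Flange covered, no active leak, but not small and localized, or not adherent | Surgery | No instruction | Gap in Table 6 |

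The direct contradiction is confined to situation 3. Situation 4 is an omission rather than a conflict.

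**Does any other text resolve it?** Leaving out the contents lists, seven places name conjunctival erosion: the Version 5 rationale, Section 4.5.9 (video recording), Section 5.1.3.3, Section 5.1.5.5, Table 6, Section 5.2.3, and SAP Section 4.7.1. Two of the seven, Section 5.1.3.3 and Table 6, say how to manage it. None says which of those two takes precedence.

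**Comparison with retraction.** Section 5.1.3.4 uses the same form of surgery sentence for conjunctival retraction. Table 6's retraction row also directs surgery and has no observation branch. Those two texts agree, so the mismatch is specific to erosion and not a general difference between the risk and management sections.

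**The term *full thickness*.** The two uses can be made compatible. Section 1.3 places the flange beneath both the conjunctiva and Tenon's capsule, so Table 6 may mean loss of all the tissue over the flange, while Section 5.1.3.3 means loss of the conjunctiva alone. The protocol does not say this. On that reading situation 3 still conflicts: a defect through the conjunctiva with the flange still covered meets the definition in Section 5.1.3.3 and, if the other conditions hold, also falls under Table 6's observation instruction.

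**The case against.** Four points can be made on the other side.

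- **The passages have different functions.** Section 5.1.3.3 is a risk description and Table 6 is the management guide. A site would naturally turn to the specific, tiered table. That is a fair account of likely practice, but Section 5.1.5.5 only points to the table and calls its content recommended, while Section 5.1.3.3 is itself worded as an instruction. Precedence is nowhere stated.
- **The Medical Monitor sees every case.** This is true and is a real mitigation. It does not separate the two rules, because both contain the step. In Section 5.1.3.3 the discussion comes before surgery and does not make surgery optional. The Medical Monitor also reads the same two instructions.
- **Section 5.1.3.3 allows for necessity.** The qualifier "permit early medical or surgical intervention, if necessary" belongs to the preceding sentence, on monitoring for signs of erosion. The surgery sentence that follows carries no such limit.
- **Some lesions under observation may be less than full thickness, and so outside Section 5.1.3.3.** If Table 6 uses erosion in that wider sense, the conflict would not reach those lesions. But Table 6 labels the row with the same event name that Section 5.1.3.3 defines, and gives no wider definition. If a wider sense was meant, one event term has two meanings, which also needs correcting. A full-thickness conjunctival defect with the flange covered remains in conflict on either reading.

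It also stands that the subset is narrow, that its frequency is unknown, and that no statistical property of the trial is touched.

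**Conclusion.** The contradiction holds. For one subset of conjunctival erosion, fixed by the five conditions in Table 6, the current protocol directs both surgery and observation and does not say which governs. This rests on reading the word erosion in Table 6 with the definition given in Section 5.1.3.3, which is the only definition the protocol supplies.

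The size in patients cannot be stated, because neither document gives an erosion rate. All 418 patients had been recruited by Version 5, so the reach is erosions managed under that version. It should be fixed because it concerns the safety of an implanted eye and costs little to correct.

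**What to change.** The sponsor's medical team must reconcile Section 5.1.3.3 with Table 6 so that each erosion situation, including the one on which Table 6 is silent, has a single instruction. *Full thickness* needs one stated meaning across both places. Sites and Medical Monitors should be told of the change. Which clinical rule is right is for the sponsor's medical team to decide.

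The cost is a wording amendment in two places and a letter. No analysis changes, and this point needs no SAP edit.

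Two lesser wording differences could be aligned in the same amendment:

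- **Implant flush in endophthalmitis:** permissive in Section 5.1.3.6, directive in Table 8.
- **Steroid drops after insertion and explantation:** required in Section 5.1.1 and Appendix 17, whereas footnote t of Appendix 1 Table 1 and footnote n of Appendix 1 Table 2 only permit anti-inflammatory drops. SAP Appendix 2 reproduces those footnotes, so aligning them would also mean a text edit there, again with no effect on any analysis.

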# 5.1.3.4 Conjunctival Retraction

The *PDS* implant and/or its procedures have been associated with conjunctival retraction (defined as a recession or opening of the limbal and/or radial peritomy). These events may be clinically relevant especially if the implant becomes exposed, and could be associated with an increased risk of endophthalmitis. The tissue overlying the PDS implant flange should be monitored carefully following the implant insertion and refill-exchange procedures to identify early signs of retraction, and permit early medical or surgical intervention, if necessary. After discussion with the Medical Monitor, surgical intervention (e.g., conjunctival/Tenon's capsule repair) should be performed in case of conjunctival retraction with or without exposure of the implant flange.

Close adherence to the most up-to-date PDS IFU *document* (e.g., appropriate suturing of conjunctiva and Tenon's capsule to the limbus, etc.) is required to minimize risks of conjunctival retraction.

# 5.1.3.5 Rhegmatogenous Retinal Detachment

The PDS implant and/or its procedures have been associated with rhegmatogenous retinal detachment. These events are clinically relevant and may result in vision loss if not promptly treated with an intervention (e.g., pneumatic retinopexy, vitrectomy, or *laser photocoagulation*). Careful evaluation of the retinal periphery by scleral indentation should be performed, and any suspected areas of abnormal vitreo-retinal adhesion or retinal breaks should be treated before inserting the implant in the eye.

Close adherence to the most up-to-date PDS IFU document (e.g., appropriate management of vitreous prolapse after pars plana incision, etc.) is required to minimize risks of rhegmatogenous retinal detachment.

## 5.1.3.6 Endophthalmitis

The PDS implant and/or *its procedures have been associated with endophthalmitis*. These events are clinically relevant and require prompt treatment as per standard of care to reduce risk of vision loss and maximize recovery (e.g., intravitreal vancomycin and ceftazidime, as well as *topical and/or oral antibiotics*, for bacterial endophthalmitis). Saline flush of the implant content using the refill needle, followed by implant *flush* with 100  $\mu l$  of vancomycin (1.0 mg/mL) may also be performed as additional treatment.

Close adherence to the most up-to date PDS IFU document (e.g., appropriate sterile controls during implant insertion or refill-exchange procedures) is required to minimize risks of endophthalmitis.

## 5.1.3.7 Device Dislocation

The PDS implant and/or its procedures have been associated with device dislocation. The implant may dislocate or subluxate into the vitreous cavity, or may extend outside the vitreous cavity into or beyond the subconjunctival space. These events are clinically relevant and, in some cases, may require urgent surgical intervention to prevent vision loss. After discussion with the Medical Monitor, urgent surgical intervention should be performed if device dislocation is associated with a positive Seidel test, retinal detachment, appositional choroidal detachment, dislocated implant resting on or near the macula, conjunctival opening with vitreous leak and implant expulsion (open globe).

Close adherence to the most up-to-date PDS IFU document (e.g., appropriate scleral incision length, appropriate targeting of the pars plana with during laser ablation) is required to minimize risks of device dislocation.

Refer to the PDS Investigator's Brochure for further information.

## 5.1.4 Potential Risks Associated with Ranibizumab Administered as an Intravitreal Injection

## 5.1.4.1 Glaucoma

Sustained IOP increase can be associated with the development of glaucoma, which in turn can lead to permanent vision loss. Although sustained increases in IOP have been reported following administration of VEGF inhibitors, there is no conclusive evidence to date that these IOP increases develop into glaucoma.

## 5.1.4.2 Venous Thromboembolic Events

Venous thromboembolic events are generally clinically relevant, ranging from superficial phlebitis to a potentially fatal pulmonary embolism. VEGF inhibition, especially systemically, could contribute to the development of this event.

## 5.1.4.3 Non-Myocardial Arterial Thromboembolic Events

ATEs may be associated with VEGF inhibition in the vascular system, as well as with underlying abnormal blood vessels due to medical conditions, such as hypertension, atherosclerosis, or diabetes.

## 5.1.4.4 Myocardial Infarction

Myocardial infarction is a clinically relevant event, ranging from an asymptomatic event to a fatal outcome.

## 5.1.4.5 Non-Ocular Hemorrhage

Non-ocular hemorrhage is a heterogeneous risk, ranging from events such as mild nose bleed to fatal gastrointestinal hemorrhage. These events may be related to the systemic effects of anti-VEGF treatment.

## 5.1.4.6 Hypertension

Hypertension may be caused by VEGF inhibition, especially when anti-VEGF agents are used systemically.

Refer to the PDS Investigator's Brochure for further information.

**Port Delivery System with Ranibizumab—F. Hoffmann-La Roche Ltd.** 78/Protocol GR40548, Version 5

## 5.1.5 Management of Patients Who Experience Adverse Events

#### 5.1.5.1 Dose Modifications

No dose modifications will be permitted in this study.

### 5.1.5.2 Treatment Interruption

Study treatment dose (*refill-exchange or intravitreal ranibizumab injection*) interruption and/or study treatment discontinuation or study discontinuation following an adverse event will be determined according to the criteria in Table 4. *The investigator should contact the Medical Monitor if the study treatment dose is interrupted and delay of treatment is to be considered for conditions outside of those specified in Table* 4. The reason for interrupting the treatment should be recorded on the associated eCRF and, if applicable, on the Adverse Event eCRF.

# Table 4Dose Interruption, Study Treatment Discontinuation, or Study
Discontinuation Criteria

Event	Dose Interruption Criteria
Intraocular inflammation	Interrupt dose if intraocular inflammation is $\geq 2+$ in the study eye (see the definitions of intraocular inflammation in Section 5.1.2.3). Study treatment may be delayed or the patient may be discontinued from study treatment after consultation with the Medical Monitor.
BCVA decrease	Interrupt dose if there is a study drug–related decrease of $\geq$ 30 letters in BCVA in the study eye compared with the last assessment of BCVA.
Elevated IOP	Interrupt ranibizumab study treatment via intravitreal injection if pre-treatment IOP in the study eye is $\geq$ 30 mmHg. Treatment will be permitted when IOP has been lowered to < 30 mmHg, either spontaneously or by treatment, as determined by the investigator. Note: In the implant arm, if IOP in the study eye is $\geq$ 30 mmHg at an implant refill-exchange visit, study treatment may proceed if the implant is seated in correct position.
Rhegmatogenous retinal break or detachment and macular hole Stages 3 or 4	Interrupt dose if a retinal break is present in the study eye. Treatment may be resumed $\geq 28$ days after the retinal break has been successfully treated. Patients with a rhegmatogenous retinal detachment or Stage 3 or 4 macular holes may require discontinuation from study treatment after consultation with the Medical Monitor.
Local or systemic infection	Interrupt dose if any of the following are present: infectious conjunctivitis, infectious keratitis, infectious scleritis, or endophthalmitis in either eye. Dose should be interrupted if the patient is currently under observation or receiving treatment for a suspected or confirmed severe systemic infection per clinical judgment (including COVID-19).
IV corticosteroids	Dose may be interrupted after consultation with the Medical Monitor if patients need to receive IV corticosteroids. Study treatment may be resumed when the patient has finished IV corticosteroid course.
Intraocular surgery	Dose may be interrupted after consultation with the Medical Monitor if intraocular surgery (except cataract, see Section 4.4.1) has been performed in the study eye within the previous 28 days.
Observed damage to the implant	If damage to the implant is observed by the investigator, the implant may be explanted even if it did not cause any adverse event to the patient. The patient may be discontinued from the study treatment.
Pregnancy	Discontinue patient's study treatment in the case of positive serum pregnancy test during the study. For patients in the implant arm, a saline flush of implant content may be performed to remove drug from the implant, after consultation with the Medical Monitor.

BCVA=best-corrected visual acuity; IOP=intraocular pressure.

# 5.1.5.3 Supplemental Treatment with Intravitreal Ranibizumab for Implant Patients

Patients randomized to the implant arm will be eligible for supplemental treatment with ranibizumab (0.5 mg intravitreal injections of 10-mg/mL formulation) at Weeks 16 and 20 (after implant insertion) and at Weeks 40, 44, 64, 68, 88, and 92 if any of the following criteria are met in the study eye:

• Decrease of ≥15 letters from the best-recorded BCVA in the study, due to nAMD disease activity

• Increase of  $\ge$  150  $\mu$ m in central subfield thickness (CST) on SD-OCT from the lowest CST measurement in the study, due to nAMD disease activity

• Increase of  $\geq$  100  $\mu$ m in CST on SD-OCT from the lowest CST measurement in the study associated with a decrease of  $\geq$  10 letters from the best recorded BCVA during the study, due to nAMD disease activity

At each visit in which supplemental treatment is possible, the study eye BCVA score and CST value must be entered into IxRS to assess the need for supplemental treatment. If any of the criteria above are met, the supplemental treatment must be administered at the end of the visit. If treatment cannot be administered at the end of the visit, patients will be asked to return within 7 days to receive supplemental treatment.

Following supplemental treatment with intravitreal ranibizumab 0.5 mg, patients will continue with scheduled implant refill-exchanges at Weeks 24, 48, and 72 relative to the Day 1 visit.

Note: Supplemental treatment is allowed at Weeks 16 and 20 (after implant insertion) and at Weeks 40, 44, 64, 68, 88 and 92 only if any of the criteria *listed* above are met. Supplemental treatment is not allowed at any other study visits. Patients with progressive worsening of nAMD disease activity (e.g., BCVA or CST worsening, new macular hemorrhage) who, in the investigator's judgment, require any treatment for nAMD in the study eye outside of protocol (e.g., ranibizumab intravitreal injection treatment at Week 8) will be discontinued from study treatment (i.e., no additional refill-exchanges) after discussion with the Medical Monitor. Patients discontinuing study treatment will be encouraged to attend as many scheduled study visits as possible, with an emphasis on completing the Week 36, Week 40, and Week 96 visits (see Appendix 4 for the minimum required assessments to be performed).

## 5.1.5.4 Recommended Management of Cases of Vitreous Hemorrhage

*The recommended management of patients with* vitreous hemorrhage secondary to implant-related procedures throughout the study *is presented* in Table 5.

Timing	Patient's Examination and Management Guidelines
Day of vitreous hemorrhage diagnosis	• If the diagnosis of vitreous hemorrhage is made during a scheduled visit and the view of the vitreous cavity is limited , perform ocular B-scan ultrasonography if possible in addition to the assessments scheduled for that specific visit.
	• If the diagnosis of vitreous hemorrhage is made during an unscheduled visit and the view of the vitreous cavity is limited , perform ocular B-scan ultrasonography if possible in addition to the assessments listed in Appendix 4.
	• A safety assessment visit (scheduled or unscheduled) should be performed approximately 2 weeks after occurrence of vitreous hemorrhage (see Appendix 4). If possible, perform ocular B-scan ultrasonography if the view of the vitreous cavity is limited.
Approximately 4 weeks after occurrence (scheduled visit)	• If possible, perform ocular B-scan ultrasonography if the view of the vitreous cavity is limited, in addition to the assessments scheduled for that specific visit.
	
 
An unscheduled safety assessment visit should be performed between 4 and 8 weeks after occurrence of vitreous hemorrhage (Appendix 4).
 

Approximately 8 weeks after occurrence (scheduled visit)	• If possible, perform ocular B-scan ultrasonography if the view of the vitreous cavity is limited.
	
 
If vitreous hemorrhage causes loss in BCVA and neither assessment of the macula nor SD-OCT can be performed successfully:
 

	
 
Discuss a pars plana vitrectomy with the patient as a possibility to remove the vitreous hemorrhage. Consultation with the Medical Monitor is advised prior to performing pars plana vitrectomy.
 

